11.8. Pharmacokinetic/Pharmacodynamic Analyses

If sufficient data are available, then other pharmacokinetic/pharmacodynamic modeling may be performed, including exploring the relationship between serum concentrations of daratumumab and endpoints of clinical efficacy and safety. If performed, details and results of the analysis will be presented in a separate report.

11.9. Patient-reported Outcomes

The modified-CTSQ item scores and Satisfaction with Therapy domain score will be summarized for each time point, by treatment arm and descriptively reported. Mean Satisfaction with Therapy domain score will be compared between treatment arms at each time point.

11.10. Medical Resource Utilization Analyses

Medical resource utilization will be descriptively summarized by treatment group. Additional analyses may be conducted; details and results of any additional analyses will be presented in a separate report.

11.11. Safety Analyses

Adverse Events

The verbatim terms used in the eCRF by investigators to identify adverse events will be coded using the Medical Dictionary for Regulatory Activities (MedDRA). Treatment-emergent adverse events are adverse events with onset during the Treatment Phase or that are a consequence of a pre-existing condition that has worsened since baseline. All reported adverse events will be included in the analysis. For each adverse event, the percentage of subjects who experience at least 1 occurrence of the given event will be summarized by treatment group. In addition, comparisons between treatment groups will be provided if appropriate.

Summaries, listings, datasets, or subject narratives may be provided, as appropriate, for those subjects who die, who discontinue treatment due to an adverse event, or who experience a severe or a serious adverse event.

Clinical Laboratory Tests

Laboratory data will be summarized for each treatment group by type of laboratory test. Reference ranges and markedly abnormal results (specified in the Statistical Analysis Plan) will be used in the summary of laboratory data. Descriptive statistics will be calculated for each laboratory analyte at baseline and for observed values and changes from baseline at each scheduled time point. Changes from baseline results will be presented in pre- versus post-treatment cross-tabulations (with classes for below, within, and above normal ranges). A listing of subjects with any laboratory results outside the reference ranges will be provided. A listing of subjects with any markedly abnormal laboratory results will also be provided.

Parameters with predefined NCI-CTCAE toxicity grades will be summarized. Change from baseline to the worst adverse event grade experienced by the subject during the study will be provided as shift tables.

Electrocardiogram (ECG)

Electrocardiogram data will be summarized based on categories of normal, abnormal either clinically significant or not clinically significant and listed.

Vital Signs

Descriptive statistics of temperature, pulse/heart rate, respiratory rate, and blood pressure (systolic and diastolic) values and changes from baseline will be summarized at each scheduled time point. The percentage of subjects with values beyond clinically important limits will be summarized.

Physical Examination

Physical examination findings will be summarized at baseline. Descriptive statistics will be calculated. Frequency tabulations of the abnormalities will be made.

11.12. Safety Data Monitoring

An IDMC, consisting of 2 clinicians and 1 statistician, will be established to review safety data periodically. The details will be provided in a separate IDMC charter.

12. ADVERSE EVENT REPORTING

Timely, accurate, and complete reporting and analysis of safety information from clinical studies are crucial for the protection of subjects, investigators, and the sponsor, and are mandated by regulatory agencies worldwide. The sponsor has established Standard Operating Procedures in conformity with regulatory requirements worldwide to ensure appropriate reporting of safety information; all clinical studies conducted by the sponsor or its affiliates will be conducted in accordance with those procedures.

12.1. Definitions

12.1.1. Adverse Event Definitions and Classifications

Adverse Event

An adverse event is any untoward medical occurrence in a clinical study subject administered a medicinal (investigational or non-investigational) product. An adverse event does not necessarily have a causal relationship with the treatment. An adverse event can therefore be any unfavorable and unintended sign (including an abnormal finding), symptom, or disease temporally associated with the use of a medicinal (investigational or non-investigational) product, whether or not related to that medicinal (investigational or non-investigational) product. (Definition per International Council for Harmonisation [ICH]).

This includes any occurrence that is new in onset or aggravated in severity or frequency from the baseline condition, or abnormal results of diagnostic procedures, including laboratory test abnormalities.

Note: The sponsor collects adverse events starting with the signing of the ICF (refer to Section 12.3.1, All Adverse Events, for time of last adverse event recording).

Serious Adverse Event

A serious adverse event based on ICH and EU Guidelines on Pharmacovigilance for Medicinal Products for Human Use is any untoward medical occurrence that at any dose:

- Results in death
- Is life-threatening
(The subject was at risk of death at the time of the event. It does not refer to an event that hypothetically might have caused death if it were more severe.)
- Requires inpatient hospitalization or prolongation of existing hospitalization
- Results in persistent or significant disability/incapacity
- Is a congenital anomaly/birth defect
- Is a suspected transmission of any infectious agent via a medicinal product
- Is Medically Important*

*Medical and scientific judgment should be exercised in deciding whether expedited reporting is also appropriate in other situations, such as important medical events that may not be immediately life threatening or result in death or hospitalization but may jeopardize the subject or may require intervention to prevent one of the other outcomes listed in the definition above. Examples of such medical events include allergic bronchospasm requiring intensive treatment in an emergency room or at home, blood dyscrasias or convulsions that do not result in hospitalization; or development of drug dependency or drug abuse or malignancy. These should usually be considered serious.

If a serious and unexpected adverse event occurs for which there is evidence suggesting a causal relationship between the study drug and the event (eg, death from anaphylaxis), the event must be reported as a suspected unexpected serious adverse reaction (SUSAR) even if it is a component of the study endpoint (eg, all-cause mortality).

Unlisted (Unexpected) Adverse Event/Reference Safety Information

An adverse event is considered unlisted if the nature or severity is not consistent with the applicable product reference safety information. The expectedness of an adverse event will be determined by whether or not it is listed in the daratumumab Investigator's Brochure (IB daratumumab¹⁰). Anticipated events will be recorded and reported as described in [Attachment 12](#).

Adverse Event Associated With the Use of the Drug

An adverse event is considered associated with the use of the drug if the attribution is possible, probable, or very likely by the definitions listed in Section [12.1.2](#), Attribution Definitions.

12.1.2. Attribution Definitions

Not Related

An adverse event that is not related to the use of the drug.

Doubtful

An adverse event for which an alternative explanation is more likely, eg, concomitant drug(s), concomitant disease(s), or the relationship in time suggests that a causal relationship is unlikely.

Possible

An adverse event that might be due to the use of the drug. An alternative explanation, eg, concomitant drug(s), concomitant disease(s), is inconclusive. The relationship in time is reasonable; therefore, the causal relationship cannot be excluded.

Probable

An adverse event that might be due to the use of the drug. The relationship in time is suggestive (eg, confirmed by dechallenge). An alternative explanation is less likely, eg, concomitant drug(s), concomitant disease(s).

Very Likely

An adverse event that is listed as a possible adverse reaction and cannot be reasonably explained by an alternative explanation, eg, concomitant drug(s), concomitant disease(s). The relationship in time is very suggestive (eg, it is confirmed by dechallenge and rechallenge).

12.1.3. Severity Criteria

The severity assessment for an adverse event or serious adverse event should be completed using NCI-CTCAE Version 4.03. Any adverse event or serious adverse event not listed in that

document will be graded according to investigator clinical judgment by using the standard grading outlined in the NCI-CTCAE Version 4.03.

The investigator should use clinical judgment in assessing the severity of events not directly experienced by the subject (eg, laboratory abnormalities).

12.2. Special Reporting Situations

Safety events of interest on a sponsor study drug that may require expedited reporting or safety evaluation include, but are not limited to:

- Overdose of a sponsor study drug
- Suspected abuse/misuse of a sponsor study drug
- Accidental or occupational exposure to a sponsor study drug
- Any failure of expected pharmacologic action (ie, lack of effect) of a sponsor study drug
- Unexpected therapeutic or clinical benefit from use of a sponsor study drug
- Medication error involving a sponsor product (with or without subject/patient exposure to the sponsor study drug, eg, name confusion)
- Exposure to a sponsor study drug from breastfeeding

Special reporting situations should be recorded in the eCRF. Any special reporting situation that meets the criteria of a serious adverse event should be recorded on the serious adverse event page of the eCRF.

12.3. Procedures

12.3.1. All Adverse Events

All adverse events and special reporting situations, whether serious or non-serious, will be reported from the time a signed and dated ICF is obtained until 30 days after the final dose of study drug during the data collection period. The only exception is for subjects who have withdrawn informed consent for study participation or for subjects who have received additional treatment with therapeutic intent for multiple myeloma within 30 days after the final dose of Dara-IV or Dara-SC. For subjects who have received additional treatment with therapeutic intent for multiple myeloma during the adverse event reporting period, only adverse events that are considered to be possibly, probably, or definitely related to study drug must be reported (unless the subject has been withdrawn from the study).

Serious adverse events, including those spontaneously reported to the investigator within 30 days after the last dose of study drug, and those that are considered related to study drug within the Follow-up Phase, must be reported using the Serious Adverse Event Form. The sponsor will evaluate any safety information that is spontaneously reported by an investigator beyond the time frame specified in the protocol.

Death should not be recorded as an adverse event or serious adverse event, but as the outcome of an adverse event. The event that resulted in the death should be reported as a serious adverse event. All events that meet the definition of a serious adverse event will be reported as serious adverse events, regardless of whether they are protocol-specific assessments. Anticipated events will be recorded and reported as described in [Attachment 12](#). Note: Some countries require reporting of all adverse events to the health authorities, while others will not identify anticipated events for the health authorities.

All adverse events, regardless of seriousness, severity, or presumed relationship to study drug, must be recorded using medical terminology in the source document and the eCRF. Whenever possible, diagnoses should be given when signs and symptoms are due to a common etiology (eg, cough, runny nose, sneezing, sore throat, and head congestion should be reported as "upper respiratory infection"). Investigators must record in the eCRF their opinion concerning the relationship of the adverse event to study therapy. All measures required for adverse event management must be recorded in the source document and reported according to sponsor instructions.

The sponsor assumes responsibility for appropriate reporting of adverse events to the regulatory authorities. The sponsor will also report to the investigator (and the head of the investigational institute where required) all suspected unexpected serious adverse reactions (SUSARs). For anticipated events reported as individual serious adverse events the sponsor will make a determination of relatedness in addition to and independent of the investigator's assessment. The sponsor will periodically evaluate the accumulating data and, when there is sufficient evidence and the sponsor has determined there is a reasonable possibility that the drug caused a serious anticipated event, they will submit a safety report in narrative format to the investigators (and the head of the investigational institute where required). The sponsor assumes responsibility for appropriate reporting of anticipated events to the regulatory authorities according to requirements of the countries in which the studies are conducted. The investigator (or sponsor where required) must report SUSARs to the appropriate Independent Ethics Committee/Institutional Review (ICE/IRB) that approved the protocol unless otherwise required and documented by the IRB/IEC.

The subject (or their designee, if applicable) must be provided with a "wallet (study) card" and instructed to carry this card with them for the duration of the study indicating the following:

- Study number
- Statement, in the local language(s), that the subject is participating in a clinical study
- Investigator's name and 24-hour contact telephone number
- Local sponsor's name and 24-hour contact telephone number (for medical staff only)
- Site number
- Subject number
- Blood type and IAT (as described in [Section 9.7](#), Safety Evaluations).

12.3.2. Serious Adverse Events

All serious adverse events occurring during the study must be reported to the appropriate sponsor contact person by study-site personnel within 24 hours of their knowledge of the event.

Information regarding serious adverse events will be transmitted to the sponsor using the Serious Adverse Event Form, which must be completed and signed by a physician from the study site, and transmitted to the sponsor within 24 hours. The initial and follow-up reports of a serious adverse event should be made by facsimile (fax).

All serious adverse events that have not resolved by the end of the study, or that have not resolved upon discontinuation of the subject's participation in the study, must be followed until any of the following occurs:

- The event resolves
- The event stabilizes
- The event returns to baseline, if a baseline value/status is available
- The event can be attributed to agents other than the study drug or to factors unrelated to study conduct
- It becomes unlikely that any additional information can be obtained (subject or health care practitioner refusal to provide additional information, lost to follow-up after demonstration of due diligence with follow-up efforts)

Suspected transmission of an infectious agent by a medicinal product will be reported as a serious adverse event. Any event requiring hospitalization (or prolongation of hospitalization) that occurs during the course of a subject's participation in a study must be reported as a serious adverse event, except hospitalizations for the following:

- Hospitalizations not intended to treat an acute illness or adverse event (eg, social reasons such as pending placement in long-term care facility)
- Surgery or procedure planned before entry into the study (must be documented in the eCRF). Note: Hospitalizations that were planned before the signing of the ICF, and where the underlying condition for which the hospitalization was planned has not worsened, will not be considered serious adverse events. Any adverse event that results in a prolongation of the originally planned hospitalization is to be reported as a new serious adverse event.
- A standard procedure for protocol therapy administration will not be reported as a serious adverse event. In addition, hospitalization due to a longer than anticipated infusion time. Hospitalization or prolonged hospitalization for a complication of therapy administration will be reported as a serious adverse event.
- The administration of blood or platelet transfusions. Hospitalization or prolonged hospitalization for a complication of such transfusion remains a reportable serious adverse event.
- A procedure for protocol-related investigations (eg, scans, endoscopy, sampling for laboratory tests, bone marrow sampling, pharmacokinetic, or biomarker blood sampling).

Hospitalization or prolonged hospitalization for a complication of such procedures remains a reportable serious adverse event.

Refer to [Attachment 13](#) for details on serious adverse event reporting after the end of the data collection period.

12.3.3. Disease-Related Events or Outcomes Not Qualifying as Adverse Events

Known consequences of the underlying disease under investigation (eg, symptoms) and events common in the study population independent of drug therapy are adverse events. If they are considered drug-related they will be recorded and reported (if appropriate) as per current legislation to Health Authorities and ECs. If they are considered disease-related or not related to the study drugs they will be exempt from expedited reporting.

12.3.4. Pregnancy

All initial reports of pregnancy in female subjects or partners of male subjects must be reported to the sponsor by the study-site personnel within 24 hours of their knowledge of the event using the appropriate pregnancy notification form. Abnormal pregnancy outcomes (eg, spontaneous abortion, fetal death, stillbirth, congenital anomalies, ectopic pregnancy) are considered serious adverse events and must be reported using the Serious Adverse Event Form. Any subject who becomes pregnant during the study must be promptly withdrawn from the study and discontinue further study treatment unless the subject (or the subject's legally acceptable representative), investigator, and sponsor agree the benefits outweigh the risks to the fetus and continuation of study treatment is in the best interests of the subject. Because the effect of the study drug on sperm is unknown, pregnancies in partners of male subjects included in the study will be reported as noted above. Follow-up information regarding the outcome of the pregnancy and any postnatal sequelae in the infant will be required.

Pregnancy reporting will continue as described above after the end of the data collection period.

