3. STUDY DESIGN AND RATIONALE

3.1. Overview of Study Design

This is a Phase 3, randomized, open-label, active-controlled, multicenter study to demonstrate that the efficacy and pharmacokinetics of Dara-SC are not inferior to those for Dara-IV. The study population will consist of adults diagnosed with multiple myeloma who have received at least 3 prior lines of therapy including a PI and an IMiD, or whose disease is refractory to both a PI and an IMiD. Approximately 480 subjects will be assigned randomly to the Dara-SC group or the Dara-IV group in a 1:1 ratio. The randomization will be stratified by body weight at baseline (≤ 65 kg, 66 kg to 85 kg, >85 kg), number of prior lines of therapy (≤ 4 prior lines versus >4 prior lines), and type of myeloma (IgG versus non-IgG).

[figure not shown]
The study consists of 3 phases: a Screening Phase, a Treatment Phase, and a Follow-up Phase. A diagram of the study design is provided in Figure 1. The Screening Phase will be up to 28 days before randomization. The Treatment Phase will extend from randomization until discontinuation of study treatment. Each subject will be treated until the sponsor confirms that disease progression has occurred for that subject, the subject has unacceptable toxicity, or other reasons (refer to Section 10.1, Discontinuation of Study Treatment). The Follow-up Phase begins immediately following the End-of-Treatment Visit, and will continue until death, loss to follow up, withdrawal of consent for study participation, or end of the data collection period, whichever occurs first.

Treatment cycles are 28 days in length. The dosing schedule for both groups will be weekly for Cycles 1 and 2, every 2 weeks for Cycles 3 to 6, and every 4 weeks thereafter. Subjects who are assigned to the Dara-SC group will receive a fixed dose of Dara-SC 1800 mg (daratumumab 1800 mg co-formulated with rHuPH20 2000 U/mL). Dara-SC will be delivered by SC injection in the abdominal SC tissue in left/right locations, alternating between individual doses. All subjects in the Dara-SC group will be observed for at least 6 hours after the end of the SC injection during Cycle 1 Day 1 and, if deemed necessary by the investigator, after consecutive

injections. Subjects who are assigned to the Dara-IV group will receive Dara-IV 16 mg/kg by IV infusion pump.

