9.1.4. Follow-Up Phase

Each subject is to have a follow-up visit 8 weeks after the last dose of study treatment. Beyond 30 days after the last dose, serious adverse events considered related to study treatment will continue to be collected. For a subject who discontinues study treatment before disease progression, disease evaluations should continue to be performed as specified in the Time and Events Schedule. After disease progression is documented, survival status, subsequent anticancer treatment, response to subsequent anticancer treatment, and date of progression will be recorded. Information on all new second primary malignancies will also be collected until the end of the data collection period. If the information is obtained via telephone contact, then written documentation of the communication must be available for review in the source documents. If the subject has died, then the date and cause of death will be collected and documented on the eCRF.

Follow-up will continue until the end of the data collection period, approximately 24 months after the last subject was randomized or when median overall survival for both arms has been reached, whichever occurs first.

Continuation of Follow-up Phase study procedures is not required once the end of the data collection period is reached, and the End of Trial page of the eCRF should be completed at that time for subjects ongoing in the Follow-up Phase.

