
M-protein levels need to meet the definition of disease progression (see [Table 5](#)) for subjects to have disease progression. Disease evaluations will continue beyond relapse from CR until disease progression is confirmed.

Disease progression must be consistently documented across clinical study sites using the criteria in [Table 5](#). It is important that instances of disease progression be reported to the sponsor as soon as possible. Diagnosis and documentation of disease progression will be reported to the sponsor within 24 hours of suspected disease progression. The medical monitor will review the information to confirm that the IMWG criteria for disease progression have been met. If the medical monitor agrees that disease progression has occurred, then a confirmation will be returned to the investigator, and the subject will be withdrawn from study treatment. If the medical monitor considers that the IMWG criteria for disease progression have not been met, then the medical monitor will contact the investigator to discuss the subject.

For continuation of treatment, the IMWG response will be determined on an ongoing basis by the investigator. For data analysis and reporting, however, the sponsor will use a validated computer algorithm that has been shown to provide consistent review of the data necessary to determine disease progression and response according to IMWG criteria.

For subjects who discontinue study treatment before disease progression, disease evaluations should continue to be performed as described in the Time and Events Schedule, until confirmed disease progression, death, start of a new treatment for multiple myeloma, withdrawal of consent for study participation, or the end of the data collection period, whichever occurs first. Blood and urine for disease evaluations scheduled for treatment days should be collected before study treatment is administered.

Refer to [Attachment 13](#) details on efficacy evaluations after the end of the data collection period.

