10. SUBJECT DISCONTINUATION OF STUDY TREATMENT/ WITHDRAWAL FROM THE STUDY

10.1. Discontinuation of Study Treatment

Discontinuation of Study Treatment

If a subject's study treatment must be discontinued, this will not result in automatic withdrawal of the subject from the study. The End-of-Treatment Visits and Follow-up visit assessments should continue as specified in the Time and Events Schedule.

A subject's study treatment must be discontinued if:

- The investigator believes that for safety or tolerability reasons (eg, adverse event) it is in the best interest of the subject to discontinue study treatment.
- The subject becomes pregnant unless the subject (or the subject's legally acceptable representative), investigator, and sponsor agree the benefits outweigh the risks to the fetus and continuation of study treatment is in the best interests of the subject
- The subject (or the subject's legally acceptable representative) withdraws consent for administration of study drug
- The subject experiences unacceptable toxicity, including IRRs described in Section 6.4, Management of Injection-site and Infusion-related Reactions
- The subject's dose is held for more than 28 days, or if 3 consecutive planned doses of daratumumab are missed for reasons other than toxicity unless, upon consultation with the sponsor and the review of safety and efficacy, continuation is agreed upon
- The subject experiences disease progression (please see below); relapse from CR is not considered as disease progression
- The subject experiences a second primary malignancy that cannot be treated by surgery alone (however, a subject who develops a malignancy that can be cured surgically may continue to receive the assigned study treatment and should continue to be followed for subsequent progression of multiple myeloma)

The primary reason for discontinuation of study treatment will be recorded in the eCRF.

Study treatment will continue until confirmation of PD. Before subjects are discontinued from study treatment because of suspected PD:

1. The investigator (or designee) will provide documentation of disease progression (for example, by completing a disease progression form or by contacting the IWRS) as soon as possible and within 48 hours of confirmation of disease progression.

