2. The sponsor's medical monitor will review the provided documentation and confirm PD has occurred per IMWG criteria (see Section 9.2.1, Response Categories) and that study treatment should be discontinued.
3. After confirmation of PD by the sponsor, the subject will discontinue study treatment and enter the Follow-up Phase.

If a subject's study treatment must be discontinued, this will not result in automatic withdrawal of the subject from the study; instead, the subject will enter the Follow-up Phase. The End-of-Treatment Visit and Follow-up Visit assessments should continue as specified in the Time and Events Schedule.

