10.2. Withdrawal From the Study

A subject will be withdrawn from the study for any of the following reasons:

- Lost to follow-up
- Withdrawal of consent
- Death
- Sponsor terminates the study

Before a subject is considered lost to follow-up, every reasonable effort must be made by the study-site personnel to contact the subject and determine the reason for discontinuation/withdrawal. The measures taken to follow up must be documented.

When a subject withdraws before completing the study, the reason for withdrawal is documented in the eCRF and in the source document. Study drug assigned to the withdrawn subject may not be assigned to another subject. If subjects withdraw from the study, additional subjects will not be enrolled. If a subject discontinues study drug and withdraws from the study before the end of the Treatment Phase, End-of-Treatment assessments should be obtained. If the withdrawal from the study is withdrawal of consent then no additional assessments are allowed.

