### 5.2.2. Estimand

The primary estimand, the main clinical quantity of interest to be estimated in the study, is defined by the following 4 components:

- Population: subjects with relapsed or refractory multiple myeloma who have received at least 3 prior lines of therapy including a PI and an IMiD, or whose disease is double refractory to both a PI and an IMiD;
- Variable: overall response, which is defined as response if the best response is PR or better assessed at or prior to the start of subsequent anticancer therapy and non-response otherwise;
- Intercurrent event: Treatment discontinuation is considered as an intercurrent event for overall response and treatment policy strategy will be implement, i.e., disease assessments ignoring the treatment discontinuation will be implemented.
- Population-level summary: relative risk of overall response between two treatment groups.

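### Protocol 12.3.4 takes a pregnant subject who stops treatment out of the study, whereas 10.1 moves her into the Follow-up Phase and neither 10.2 nor 3.1 lists pregnancy as an exit reason

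*Protocol*

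**What the plan says.** Protocol 12.3.4 (Pregnancy) says that a subject who becomes pregnant "must be promptly withdrawn from the study and discontinue further study treatment unless the subject" or her representative, the investigator and the sponsor all agree that benefit outweighs fetal risk and that treatment should go on. The same section requires follow-up on the outcome of the pregnancy and on the infant.

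Protocol 10.1 (Discontinuation of Study Treatment) lists pregnancy, with the same three-party exception, among the reasons to stop study treatment. It says that stopping treatment has a limited consequence: "this will not result in automatic withdrawal of the subject from the study"; "instead, the subject will enter the Follow-up Phase". End-of-Treatment and follow-up assessments then continue on schedule.

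Protocol 10.2 opens its list with "A subject will be withdrawn from the study for any of the following reasons" and gives four: loss to follow-up, withdrawn consent, death, and termination of the study by the sponsor. Protocol 3.1 says that the Follow-up Phase "will continue until death, loss to follow up, withdrawal of consent for study participation, or end of the data collection period", whichever comes first.

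Three other places describe what should happen after treatment stops:

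- Protocol 9.2.1: "For subjects who discontinue study treatment before disease progression, disease evaluations should continue to be performed".
- Protocol 9.1.4: "Beyond 30 days after the last dose, serious adverse events considered related to study treatment will continue to be collected". Survival status, subsequent therapy and second primary malignancies are collected as well.
- SAP 5.2.2 handles treatment discontinuation for overall response by a treatment policy strategy: "disease assessments ignoring the treatment discontinuation will be implemented".

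**The concern.** Stopping the drug and leaving the study are different acts, and this protocol gives them separate subsections. Section 12.3.4 orders both for a pregnant subject; Section 10.1 orders only the first and says what follows it. A site with a pregnant subject who stops drug therefore has two incompatible instructions, one of them worded as a must.

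If the site follows 12.3.4, a randomized woman who has not withdrawn consent could lose her post-treatment disease assessments, her routine survival follow-up, and the later collection of treatment-related serious adverse events and second malignancies. PFS and OS are both in the tested secondary hierarchy (SAP 5.1.1), and both depend on follow-up after treatment ends. Under SAP Table 2, a subject who leaves without progression or death is censored for PFS at her last disease assessment, so the lost follow-up would appear as early censoring.

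There is no evident safety reason to end follow-up. Stopping the drug ends further dosing. What remains under Table 1, footnote a, is mostly blood and urine testing every 4 weeks, with a skeletal survey only as clinically indicated and post-progression information that may be taken by telephone.

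**Working it through.** No plan figure needs to be reproduced, since the point rests on comparing current protocol text. All the sections compared are in the protocol body, not in the amendment log.

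| Protocol section | Pregnant subject who stops treatment | Stays in the study? |
|---|---|---|
| 12.3.4 | Withdrawn from the study and off treatment | No |
| 10.1 | Off treatment, then Follow-up Phase | Yes |
| 10.2 | Pregnancy not among the four withdrawal reasons | Yes |
| 3.1 | Pregnancy not among the four events that end follow-up | Yes |

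1. *Can 12.3.4 be read as loose wording for stopping treatment?* Not comfortably. The sentence names study withdrawal and treatment discontinuation as two separate actions.

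2. *Does the word automatic in 10.1 leave room for 12.3.4?* No. Section 10.1 goes on to state positively that the subject enters the Follow-up Phase. She cannot both enter it and be out of the study.

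3. *Does the exception reconcile the sections?* No. It is the same in both and applies only when the three parties agree to continue treatment. Every pregnant subject who stops treatment is outside the exception and falls under both rules.

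4. *Could study withdrawal be what was intended?* If so, 10.1, 10.2 and 3.1 are the sections in error. The conflict remains either way. Because the follow-up intent is repeated in 3.1, 9.1.4, 9.2.1 and 10.1, 12.3.4 is the likelier outlier.

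5. *Does the pregnancy outcome reporting in 12.3.4 fill the gap?* No. It covers the pregnancy and the infant, not disease status, survival or second malignancies.

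Scale, from the planned sizes in Protocol 11.2 (240 per group, 480 in total):

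- Share of one group per affected subject: 1/240 = 0.00417 = 0.42%.
- Share of the planned total: 1/480 = 0.00208 = 0.21%.

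These are the weight of one subject, not an estimated bias. The documents give no expected number of pregnancies, so no effect on PFS, OS or safety rates can be calculated.

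**The case against.** The wording mismatch is hard to dispute; the case on the other side concerns its consequences.

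- *Pregnancy is strongly guarded against.* Women of childbearing potential must abstain or use two contraceptive methods and must test negative (4.1). Pregnancy or planned pregnancy is an exclusion (4.2), and contraception continues for 3 months after the last dose (4.3). The number of cases may be zero. This stands.
- *The sponsor would probably sort it out.* Each pregnancy is reported to the sponsor within 24 hours, and the sponsor is party to the decision on continuing treatment. Sections 10.1 and 10.2 are the dedicated disposition sections. This stands as a reason to call the loss possible rather than certain.
- *Other provisions limit the loss.* Section 10.2 asks for End-of-Treatment assessments when a subject stops drug and withdraws, and bars further assessments only on withdrawal of consent. Section 12.3.2 has unresolved serious adverse events followed up, 12.3.1 has the sponsor evaluate late spontaneous reports, and 9.3.4 requires samples at early discontinuation. The consent described in 16.2.3 includes permission to obtain survival status. These narrow the safety loss, but they do not restore scheduled disease assessments, routine survival follow-up or prospective collection of later related events.
- *The estimand link is weak.* SAP 5.2.2 concerns ORR only. SAP Amendment 1 (12 February 2019) already describes the planned 480 subjects as randomized, and the primary analysis comes about 6 months after that point. By inference, the cutoff fell around August 2019 at the latest, before Protocol Amendment 4 (01 April 2020). The link is a minor supporting point, and the ORR result does not turn on it.
- *This is editorial inconsistency, not a design decision.* That is a fair description of how it probably arose. The instruction is nonetheless operative, and it conflicts with the follow-up that the rest of the protocol requires.

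**Conclusion.** The concern holds. For any subject who becomes pregnant and stops treatment, Protocol 12.3.4 contradicts 10.1, and pregnancy appears in neither the 10.2 nor the 3.1 list.

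The expected effect is very small, and correcting it is desirable rather than essential. Neither co-primary conclusion is at risk. Data collected before withdrawal stay in the intent-to-treat analyses, and pregnancy and infant outcomes are still reported. What is exposed is later PFS, OS and safety follow-up in however many such subjects arise.

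Confidence in the textual conflict is high. That data would actually be lost rests on the assumption that a site follows 12.3.4 in preference to 10.1, which the documents neither show nor rule out.

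**What to change.** In Protocol 12.3.4, replace the instruction to withdraw the subject from the study and stop treatment with: *must promptly discontinue study treatment and enter the Follow-up Phase (Section 10.1)*. Keep the three-party exception and the pregnancy and infant outcome reporting unchanged. Sections 10.1, 10.2 and 3.1 need no edit.

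The cost is one phrase at the next amendment, with no visits or procedures beyond those that 10.1 already requires. A subject who does not want follow-up can still withdraw consent, which 10.2 already covers.
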